| Discharge criteria (Pages 103-104) | 
1. Defined criteria that need to be met before subject may be discharged from the CRC, including glucose measurement criteria and length of time they need to be observed after the end of the closed loop glucose control session.
 | 
1. To better describe for the study nurse the criteria that need to be met prior to discharge.
 |
| Frequency of Reference Glucose Values (Pages 103-104) | 
1. Clarified how often Reference Glucose Values will be obtained under different circumstances.
 | 
1. To clarify for study personnel the circumstances under which Reference Glucose Values will be checked every 10, 30 or 60 minutes.
 |
| Diabetic Ketoacidosis screening (Page 54) | 
1. Added criteria to screen for diabetic ketoacidosis if the Reference or Dexcom G6 CGM(s) have been greater than 200 mg/dL for more than one hour consecutively.
 | 
1. To screen for diabetic ketoacidosis if the subject is experiencing persistent hyperglycemia.
 |
| Screening prior to initiation closed loop glucose control session (Time 0 to 5 hours, page 54). | 
1. Added screening criteria to make sure subjects are not in DKA before entering the study, and to also make sure they are not acutely ill with any other illness, prior to starting the study.
 | 
1. To prevent using the FUSION system on an acutely ill or unstable subject.
 |
| Use of device – Electrostatic Discharge (Protocol 2, page 97) | 
1. Added instructions to mitigate against risk of introducing an electrostatic discharge to the FUSION system.
 | 
1. To prevent an electrostatic discharge from adversely affecting the performance of the FUSION system.
 |
| Length of use of medication syringes (time 5 to 29 hours, page 59) | 
1. Added instructions to not use the medication syringes for a period of time exceeding 24 hours.
 | 
1. To avoid using the medication syringes for a period of time exceeding 24 hours, as the biocompatibility of the medications in the syringes is unclear for a period of time exceeding 24 hours and is thus not FDA approved.
 |

NIH-FDA Phase 2 and 3 IND/IDE Clinical Trial Protocol Template

| | | |
|--|--|---|
| Necessary equipment (time 0 to 2 hours, Pages 53-54) | 
 1. Specified equipment to be on hand in the CRC, including cardiac monitor, pulse oximeter, blood pressure cuff, and resuscitation cart. | 
 1. To make sure CRC has adequate equipment on hand to both monitor and resuscitate the subject. |
| Synopsis (page 4) | 
 1. Increased study size from two type 2 diabetic subjects to two type 1 diabetic subjects and six type 2 diabetic subjects. | 
 1. To update the study size. |
| Labs (page 6) | 
 1. Added hemoglobin to screening labs | 
 1. To exclude subjects who do not have normal hemoglobin levels, given that the study subjects may have up to 80 mL of blood drawn during the course of the study. |
| Rescue Medicine (Pages 38 & 62) | 
 1. Added Glucagon | 
 1. To give additional option for treatment of hypoglycemia. |
| Meal Plan (Page 58) | 
 1. Changed closed loop control session start time to 1200 with first meal being lunch | 
 1. To allow CGM's time to warm up and verify their accuracy, prior to starting the study |
| Entire Document | 
 1. Changed length of study to 32 hours 2. Changed interval for checking Reference Glucose Values to every 10-60 minutes 3. Changed document version year to 2022 to reflect year submitted to IRB, and version number to 1.0.7 | 
 1. To ensure consistency within the document 2. To ensure consistency within the document, and to cover all possible intervals between Reference Glucose Values 3. To update document to coincide with year of submission to IRB and most recent version number |
| Protocol 1 (Page 95) | 
 1. Changed carrier solution for FUSION systems insulin and dextrose infusions from normal saline to ½ normal saline | 
 1. To reflect agreement with FDA to use a hypo-osmotic carrier solution to minimize risk of vein irritation from infusion of hyper-osmolar D10 normal saline solution used by the FUSION system |

NIH-FDA Phase 2 and 3 IND/IDE Clinical Trial Protocol Template

| | | |
|--|--|---|
| Study Data Identification (Pages 79) | 
 1. Clarified that only de-identified data will be used in the study | 
 1. To ensure protection of the study subjects and any study subject data obtained through the subject's participation in the study |
| Role of IMT Personnel (Pages 85) | 
 1. Clarified role IMT personnel will have in the study – limited to use of the FUSION system with no study subject interaction, no provision of study subject medical care, and no extraction or analysis of the study data | 
 1. To prevent IMT personnel from becoming involved in study subject medical care and to protect the integrity of the studies data for purposes of future regulatory submissions |
| Method of use of the Dexcom G6 CGM system by the FUSION system (Page 39) | 
 1. Stated that the FUSION system uses a simple average of the two Dexcom G6 CGM systems to effect glucose control. 2. Clarified that the FUSION system will continue to operate for up to 4 hours on the glucose data from only one Dexcom G6 CGM. 3. Clarified that the FUSION system will continue to operate for up to 20 minutes if no glucose data is available from either Dexcom G6 CGM system. | 
 1. To clarify for study personnel how the FUSION system uses the data from the two Dexcom G6 CGM systems. |
| Method of communication between the Dexcom G6 CGM transmitter and receiver (Page 40) | 
 1. Stated that the Dexcom G6 CGM Sensor/Transmitter pair communicate with the Dexcom G6 CGM Receiver via Bluetooth. 2. Stated that the method of communication of the Dexcom G6 CGM system has not been altered in any way by IMT personnel. | 
 1. To clarify for the study personnel that IMT has not altered, in any way, how the Dexcom G6 CGM system functions. |
| Method and accuracy of data extraction of glucose values from the Dexcom G6 CGM Receiver by the FUSION system | 
 1. Stated that the FUSION system uses a software Driver to extract the glucose values from the Dexcom G6 CGM Receiver. 2. Also noted that the FUSION system is connected to the Dexcom G6 CGM Receiver by a serial data cable. | 
 1. To clarify for study personnel how the FUSION system extracts glucose data from the Dexcom G6 CGM Receiver. 2. To clarify for study personnel that the Dexcom G6 Receiver transfers its data to the computer running the FUSION |

NIH-FDA Phase 2 and 3 IND/IDE Clinical Trial Protocol Template

| | | |
|---|---|---|
| (Page 40) | | systems software via a data cable. |
| Reference Glucose Values (Pages 37-38) | 
 1. Stated that results from the Nova StatStrip Hospital Glucose Meter System glucose meter will be used as Reference Glucose Values 2. Stated that if the retrograde hand vein is no longer available for blood draws for Reference Glucose Values, that capillary blood from a fingerstick could be used as a Reference Glucose Value. | 
 1. To clarify that only the Nova StatStrip Hospital Glucose Meter System will be used to analyze whole blood samples Reference Glucose Values. 2. To increase the likelihood of finishing the study if the retrograde hand stops functioning. |
| Human subject data (Pages 29-30) | 
 1. Listed demographic and glucose metric results from the first two subjects treated with the FUSION system, as well as glucose versus time graphs with overlayed infusion data. | 
 1. To note the performance characteristics of the FUSION system in its first in human study. |
| Risk assessment – compression artifact (Pages 30, 41, and 106) | 
 1. Noted risk of a false low glucose value from compression of the local Dexcom G6 sensor site due to subject laying on this site. 2. Documented accuracy of posterior upper arm site for Dexcom CGM in clinical study, to inform FDA of the validity of using this alternative site. 3. Clarified that the two Dexcom CGM's should be placed on contralateral sides if a replacement CGM is placed in the posterior upper arm position(e.g., right abdomen and left arm) | 
 1. To document this additional risk and clarify for the study nurse steps needed to mitigate this risk. 2. To inform FDA that the posterior upper arm site is a valid site for CGM placement. 3. To decrease risk of subject compressing both CGM's at the same time. |
| Risk assessment – Volume overload (Pages 41-42) | 
 1. Documented the tendency of the FUSION system to deliver approximately 25% of the subject's total daily fluid needs. | 
 1. To reinforce for study personnel the importance of selecting out subjects with renal or cardiac disease who are more likely to suffer side effects from volume overload. 2. To clarify for study personnel the need to monitor the |

NIH-FDA Phase 2 and 3 IND/IDE Clinical Trial Protocol Template

| | | subjects for signs of excessive volume overloading |
|--|---|---|
| Recovery Period (Pages 107-109) | 1. Defined the subcutaneous insulin dosing provided after the conclusion of the closed loop glucose control session. | 1. To clarify for study personnel the method for transitioning the subjects from the closed loop glucose control session to glucose control via subcutaneous insulin injections or CII via an insulin pump. |
| Reference Glucose Value (Throughout the document) | 1. Defined the term “Reference Glucose Value” and used consistently throughout the document. | 1. To clarify for study staff the difference between a Reference Glucose Value and a CGM glucose value. |
| CGM Placement (Pages 104-105) | 1. Noted proper position for CGM placement, including alternative placement site. | 1. To clarify for study staff the proper abdominal position for CGM placement, and to alert them of the availability of using the posterior upper arm position as an alternative placement site. |
| Instructions for Subject Prior to Visit 3 (Page 53) | 1. Clarified the timing to withhold oral anti-hyperglycemic medications prior to visit 3. | 1. To clarify for study staff and the subjects when they should begin to withhold their oral anti-hyperglycemic medications prior to visit 3. |
| Hypoglycemia Treatment (Page 62) | 1. Clarified when to treat hypoglycemia and its related symptoms. 2. Clarified the treatment methods available for hypoglycemia. 3. Defined and documented the need to treat neuroglycopenia. | 1. To clarify and educate the study staff when and how to treat hypoglycemia. |
| Halting versus Termination Criteria | 1. Removed the term “Halting Criteria” from the document. 2. Clarified the different criteria for terminating the study on one subject versus terminating the entire study. | 1. To consistently use one term (e.g., “Termination Criteria”) to signify the permanent end of the study on either one subject or the entire study. |

NIH-FDA Phase 2 and 3 IND/IDE Clinical Trial Protocol Template

| | | |
|--|---|---|
| (Throughout document) | 
3. Added excessive blood removal during visit 3 as a termination criterion (Page 102).
 
4. Added excessive volume administration from FUSION system.
 | 
2. To clarify for study staff the different criteria for terminating the study on one subject versus terminating the entire study.
 |
| Criteria to Replace CGM's (Pages 105-106) | 
1. Clarified criteria whereby the CGM(s) should be replaced.
 | 
1. To clarify this issue for study staff.
 |
| CGM Validation Criteria (Page 105) | 
1. Clarified criteria whereby the CGM should be calibrated.
 
2. Clarified that either one or both CGM's may need calibration at the same time.
 
3. Clarified that it is possible to go the entire study without calibrating the CGM's.
 | 
1. To clarify this issue for study staff.
 |
| Noted new FUSION system alarm features (Page 106) | 
1. To document the Compression Artifact and CGM Discrepancy (e.g., CGM's > 20% different than their averaged value) alarms added to the FUSION system
 | 
1. To alert study staff to these new features of the FUSION system
 |
| Added C-Peptide to study labs (Page 6) | 
1. To test for lack of endogenous insulin production in type 2 diabetic subjects.
 | 
1. To avoid inadvertent classification of type 1 diabetic subjects as type 2 diabetic subjects.
 |
| Risk Assessment (Pages 41, 44-45) | 
1. Added Volume Overload, Severe Hyperglycemia, DKA, and HHS to risk assessment section.
 | 
1. To clarify for study staff that these are risks of this study, including during the closed loop glucose control session.
 |
| Updated Exclusion Criteria (Page 50) | 
1. Added any form of renal failure or congestive heart failure to exclusion criteria.
 
2. Added low C-Peptide levels as an exclusion criteria for type 2 diabetic subjects.
 | 
1. To prevent exacerbation of an underlying chronic health condition due to excessive fluid loading from the FUSION system.
 
2. To prevent use of the FUSION system on more than two type 1 diabetic subjects.
 |

NIH-FDA Phase 2 and 3 IND/IDE Clinical Trial Protocol Template

| | | |
|---|---|---|
| Updated Care provided in visit 3 (Page 100) | 
 1. Clarified the insulin dosing given to subjects in the 5 hour period prior to starting the closed loop session on visit 3. 2. Clarified that the study nurse will give all insulin injections in the CRC. 3. Clarified that the insulin given to subjects in the CRC will be provided by the CRC (e.g., subject may not use their own insulin). | 
 1. To clarify these issues for study staff and the subjects. 2. To increase control over the care provided to the subjects during visit 3. |
| Pre-Study assessment at beginning of visit 3 (Page 54) | 
 1. Clarified the labs to be performed on the subjects prior to proceeding with the closed loop session on visit 3. 2. Documented which Ketone meter will be used during the above assessment. | 
 1. To clarify this issue for study staff. |

Table of Contents

| | |
|--|----|
| STATEMENT OF COMPLIANCE | 1 |
| 1 PROTOCOL SUMMARY | 1 |
| 1.1 Synopsis | 1 |
| 1.2 Schema | 5 |
| 1.3 Schedule of Activities (SoA) | 6 |
| 2 INTRODUCTION | 7 |
| 2.1 Study Rationale- Glycemic Control in the ICU | 7 |
| 2.2 Study rationale – COVID-19 | 11 |
| 2.3 Study rationale – Fusion AI based artificial pancreas system | 19 |
| 3 fusion system testing Background | 20 |
| 3.1 Simulation studies | 20 |
| 3.2 animal studies | 23 |
| 3.3 human study | 28 |
| 4 Risk/Benefit Assessment | 36 |
| 4.1 Known Potential Risks | 36 |
| 4.2 Known Potential Benefits | 39 |
| 4.3 Assessment of Potential Risks and benefits | 39 |
| 4.3.1 Failure of Dexcom G6 continuous glucose monitor(s) | 39 |

The trial will be carried out in accordance with International Council on Harmonisation (ICH) Good Clinical Practice (GCP) and the following:

- Applicable standards as set forth by the NIH and/or FDA.

National Institute of Health (NIH)-funded investigators and clinical trial site staff who are responsible for the conduct, management, or oversight of NIH-funded clinical trials have completed Human Subjects Protection and ICH GCP Training.

The protocol, informed consent form(s), recruitment materials, and all participant materials will be submitted to the Institutional Review Board (IRB) for review and approval. Approval of both the protocol and the consent form must be obtained before any participant is enrolled. Any amendment to the protocol will require review and approval by the IRB before the changes are implemented to the study. In addition, all changes to the consent form will be IRB-approved; a determination will be made regarding whether a new consent needs to be obtained from participants who provided consent, using a previously approved consent form.

1 PROTOCOL SUMMARY

1.1 SYNOPSIS

Title:

DEMONSTRATION OF AN ARTIFICIAL INTELLIGENCE BASED CLOSED LOOP GLUCOSE CONTROL SYSTEM AS A THERAPEUTIC MODALITY IN TYPE 1 AND TYPE 2 DIABETIC PATIENTS

Study Description:

Tight glucose control in the Intensive Care Unit (ICU) setting is difficult to achieve. We hypothesize that a closed loop glucose control system based on artificial intelligence (AI) will improve upon the glucose control currently achieved by open loop systems, and may improve the outcomes of critically ill patients, including those with COVID-19. This Early Feasibility Study (EFS) will test the ability of a prototype artificial intelligence based closed loop glucose control system named FUSION, to provide safe and effective glucose control in subjects with type 1 and type 2 diabetes in a clinical research center (CRC) setting. Subjects with type 1 diabetes have been chosen as they lack native Insulin production, which makes it

challenging to provide safe and effective glucose control for them. Subjects with type 2 diabetes have been chosen as they are insulin resistant, which makes their insulin resistance profiles like that of ICU patients. As this is a continuation of a first in human study of a new medical device, the controlled environment of the CRC is preferable to the less controlled environment of an ICU setting.

Objectives:

Primary Objectives:

1. The primary safety objective of this first in human study is to test the hypothesis that an AI based closed loop glucose control system will be able to safely control the blood glucose levels of participants with type 1 and type 2 diabetes during a 24 hour stay in the CRC setting.
2. The primary efficacy objective of this first in human study is to test the hypothesis that an AI based closed loop glucose control system will effectively control the blood glucose levels of participants with type 1 and type 2 diabetes during a 24 hour stay in the CRC setting.

Secondary Objectives:

The secondary objectives of this study are to test the hypothesis that an AI based glucose controller will be effective in minimizing glucose curve variations commonly observed in critically ill patients.

Endpoints:

Primary Endpoint:

1. The primary safety endpoint will be the percent of all glucose values that are within the glucose range of less than < 70 mg/dL. Time frame will be from start of use of AI controller until end of use of AI controller.
2. The primary efficacy endpoint will be the percent of all glucose values that are within the glucose range of 70-180 mg/dL.

DEMONSTRATION OF AN ARTIFICIAL INTELLIGENCE BASED CLOSED LOOP GLUCOSE CONTROL SYSTEM AS A THERAPEUTIC MODALITY IN TYPE 1 AND TYPE 2 DIABETIC PATIENTS

Protocol IMT 2022-1

CONFIDENTIAL

Version1.0.7

22 August 2022

Time frame will be from start of use of AI controller until end of use of AI controller.

Secondary Endpoints:

- Measure the percent of glucose values that are within clinically significant hypoglycemic range (glucose <54 mg/dL).
- Measure the percent of glucose values that are within the moderate hypoglycemic range of 54-69 mg/dL.
- Number of hypoglycemic events as measured by glucose < 70 mg/dL.
- Measure the percent of glucose values that are within the desired glucose control range of 100-140 mg/dL.
- Measure the percent of glucose values that are within the range of 70-140 mg/dL.
- Measure the percent of glucose values that are within the hyperglycemic range of >140 mg/dL.
- Measure the percent of glucose values that are within the range of 70-180 mg/dL.
- Measure the percent of glucose values that are within the hyperglycemic range of >180 mg/dL.
- Mean glucose level.
- Measure of dispersion – coefficient of variation (CV).
- The study data will be used to determine the percentage of paired glucose values (continuous glucose monitor(s) and Reference Glucose Value) in each zone using a Clarke error grid analysis.¹ These calculations will be performed for each individual CGM system and for the glucose value used by the FUSION system for purposes of glucose control (a calculated average of the two CGM systems).

Time frame will be from start of the use of AI controller until end of use of AI controller.

Study Population: Two participants with type 1 diabetes and six participants with type 2 diabetes, male and non-pregnant females, ages 18-70 inclusive, admitted to a CRC. Participants will eat three standardized meals during their 24-hour closed loop glucose control study.

DEMONSTRATION OF AN ARTIFICIAL INTELLIGENCE BASED CLOSED LOOP GLUCOSE CONTROL SYSTEM AS A THERAPEUTIC MODALITY IN TYPE 1 AND TYPE 2 DIABETIC PATIENTS

Protocol IMT 2022-1

CONFIDENTIAL

Version1.0.7

22 August 2022

Phase: Early Feasibility Study, First in Human.

Description of Sites/Facilities Enrolling Participants: Emory University Hospital, a tertiary care facility located in Atlanta, Georgia, United States. Single center study, all enrollments within USA.

Description of Study Intervention: The medical device to be tested is named FUSION and is a fully functional closed loop glucose control system (artificial pancreas). The system consists of three main components: **1)** Two Dexcom G6 continuous glucose monitors (CGM) provide glucose values to the glucose control software, **2)** Glucose control software that is run by an all in one Medical Computer that is mounted on a powered Medical Cart, and which uses an artificial intelligence technique to determine, in an iterative fashion, the infusion rates of intravenous (IV) insulin and/or dextrose into the type 2 diabetic subjects for purposes of controlling their blood glucose into the range of 100-140 mg/dL, **3)** Two syringe pumps that are used to infuse insulin and/or dextrose into the study subjects. These syringe pumps are connected by serial data cables to the Medical Computer that runs the glucose control software, and their infusion rates are controlled by the glucose control software. Reference Glucose Values are measured every 10-60 minutes on the Nova StatStrip Hospital Glucose Meter System point of care glucose meter to ensure subject safety.

Study Duration: Six months.

Participant Duration: Thirty-two hours.

DEMONSTRATION OF AN ARTIFICIAL INTELLIGENCE BASED CLOSED LOOP GLUCOSE CONTROL SYSTEM AS A THERAPEUTIC MODALITY IN TYPE 1 AND TYPE 2 DIABETIC PATIENTS

Protocol IMT 2022-1

CONFIDENTIAL

[figure not shown]
Version1.0.7

22 August 2022

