4.3.12 RISK OF HYPEROSMOLAR HYPERGLYCEMIC SYNDROME

HHS is defined as a serious complication in subjects with type 2 diabetes, and occasionally in subjects with type 1 diabetes, that occurs when the subject experiences severe hyperglycemia (usually >600 mg/dL) for a prolonged period of time. HHS may produce severe dehydration, altered level of consciousness, and coma. The risk of subjects developing HHS while they are in the study is expected to be low and will be mitigated close monitoring of the subject's Reference Glucose Values at least every 1 hour with the Nova StatStrip Hospital Glucose Meter. If the subject has a CGM value greater than 240 mg/dL (detected by CGM alarm set for glucose values > 240 mg/dL) or Reference Glucose Value greater than 240 mg/dL, the risk will be further mitigated by monitoring the subjects Reference Glucose Value every 30 minutes until their Reference Glucose Value is less than 240 mg/dL. Finally, the risk will be mitigated by terminating the study if the subjects CGM or Reference Glucose Value remains > 300 mg/dL for more than 1 hour.

The overall risks of the study are outweighed by the potential benefit of demonstrating the safety of the FUSION systems AI based glucose control software, which is the first step in testing this software with an eventual goal of using it to create a closed loop glucose control system for use in the ICU setting.

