5 OBJECTIVES AND ENDPOINTS

DEMONSTRATION OF AN ARTIFICIAL INTELLIGENCE BASED CLOSED LOOP GLUCOSE CONTROL SYSTEM AS A THERAPEUTIC MODALITY IN TYPE 1 AND TYPE 2 DIABETIC PATIENTS

Protocol IMT 2022-1

CONFIDENTIAL

Version1.0.7

22 August 2022

| OBJECTIVES | ENDPOINTS | JUSTIFICATION FOR ENDPOINTS |
|---|---|--|
| Primary | | |
| 
i. Safety
 
To assess the hypothesis that an AI based glucose controller will provide safe glucose control in participants with type 2 diabetes consuming three meals over the course of the 24-hour closed loop glucose control session.
 | 
The percent of all glucose values that are in the hypoglycemic range, when the latter is defined as glucose values less than 70 mg/dL.
 | 
Avoidance of hypoglycemia during tight glucose control leads to decreased mortality rates, and thus measurements of the rate of occurrence of hypoglycemia can be considered an assessment of the overall safety of the glucose control system under study.
 |
| 
2. Efficacy
 
To assess the hypothesis that an AI based glucose controller will provide effective glucose control in participants with type 2 diabetes consuming three meals over the course of the 24-hour closed loop glucose control session.
 | 
The percent of all glucose values that are within the range of 70-180 mg/dL.
 | 
ICU mortality rates increase when patients experience both hypoglycemia (< 70 mg/dL) and hyperglycemia (> 180 mg/dL). Thus, testing the ability of the AI based glucose control system to maintain the study subjects in the range of 70-180 mg/dL will give an indication of its ability to avoid these two deleterious glycemic states.
 |
| Secondary | | |

DEMONSTRATION OF AN ARTIFICIAL INTELLIGENCE BASED CLOSED LOOP GLUCOSE CONTROL SYSTEM AS A THERAPEUTIC MODALITY IN TYPE 1 AND TYPE 2 DIABETIC PATIENTS

Protocol IMT 2022-1

CONFIDENTIAL

Version1.0.7

22 August 2022

| OBJECTIVES | ENDPOINTS | JUSTIFICATION FOR ENDPOINTS |
|--|--|---|

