6 STUDY DESIGN

6.1 OVERALL DESIGN

Tight glucose control in the ICU setting is difficult to achieve. We hypothesize that a closed loop glucose control system based on artificial intelligence will improve upon the glucose control currently achieved by open loop systems. This non-randomized Early Feasibility First in Human Study at a single study site will test the ability of a prototype closed loop glucose control system to provide safe and effective glucose control in participants with type 1 diabetes who lack endogenous insulin production, and type 2 diabetes who have insulin resistance profiles that match those of ICU patients.⁵⁸ The study will be performed in a CRC setting on two participants with type 1 diabetes and six participants with type 2 diabetes over a time period of thirty-two hours per subject. The subjects will all consume three standardized meals during the 24-hour period their blood glucose levels are being controlled by the FUSION system. Study volunteers will be recruited from the adult endocrinology clinics of Emory University and/or Grady Hospital in Atlanta. Identified subjects who have been screened and enrolled in the study will have the study completed within two weeks of enrollment. An interim data analysis is not planned.

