11 STATISTICAL CONSIDERATIONS

A formal Statistical Analysis Plan (SAP) will not be developed for this study, thus formal null and alternative hypothesis will not be stated.

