11.1 STATISTICAL MEASUREMENTS

Primary Safety and Efficacy Endpoints:

1. Safety

The safety of the FUSION system will be determined by its ability to avoid hypoglycemia in adult type 1 and type 2 diabetic patients consuming three meals over a period of 24 hours. Safety will be measured by calculating the percent of all glucose values that are within the hypoglycemic range of less than 70 mg/dL.

Statistics – No statistical comparison will be made for this measurement.

2. Efficacy

The efficacy of the FUSION system will be determined by its ability to maintain glucose in the normal range in adult type 1 and type 2 diabetic patients consuming three meals over a period of 24 hours. Efficacy will be measured by calculating the percent of all glucose values that are within the normal glucose range of 70-180 mg/dL.

Statistics – No statistical comparison will be made for this measurement.

Secondary Efficacy Endpoints:

The secondary objectives of the study are to assess the controller's ability to minimize glucose curve measurements associated with increased ICU morbidity/mortality rates, and to maximize those measurements associated with decreased ICU morbidity/mortality rates.

1. Measure the percent of glucose values that are within the severe hypoglycemic range of 0- <54 mg/dL.

Statistics – No statistical comparison will be made for this measurement.

2. Measure the percent of glucose values that are within the moderate hypoglycemic range of 54-69 mg/dL.

Statistics – No statistical comparison will be made for this measurement.

3. Measure the number of hypoglycemic (< 70 mg/dL) events.

Statistics – No statistical comparison will be made for this measurement.

DEMONSTRATION OF AN ARTIFICIAL INTELLIGENCE BASED CLOSED LOOP GLUCOSE CONTROL SYSTEM AS A THERAPEUTIC MODALITY IN TYPE 1 AND TYPE 2 DIABETIC PATIENTS

Protocol IMT 2022-1

CONFIDENTIAL

Version1.0.7

22 August 2022

4. Measure the percent of all glucose values that are within the desired glucose control range of 100-140 mg/dL.

Statistics – No statistical comparison will be made for this measurement.

5. Measure the percent of glucose values that are within the range of 70-140 mg/dL.

Statistics – No statistical comparison will be made for this measurement.

6. Measure the percent of glucose values that are within the hyperglycemic range of > 140 mg/dL.

Statistics – No statistical comparison will be made for this measurement.

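### The synopsis promises hypothesis tests of safe and effective control, but the primary endpoints carry no criterion, and the planned median and IQR can read zero while subjects are hypoglycemic

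*Combined protocol and SAP*

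**What the plan says.** Section 1.1 states two primary objectives for subjects with type 1 and type 2 diabetes. The safety objective is "to test the hypothesis that an AI based closed loop glucose control system will be able to safely control the blood glucose levels"; the efficacy objective is "to test the hypothesis that an AI based closed loop glucose control system will effectively control the blood glucose levels". Section 5 also speaks of assessing a hypothesis, but it limits both primary objectives to type 2. Its safety objective is that the controller "will provide safe glucose control in participants with type 2 diabetes consuming three meals".

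Section 11 opens: "A formal Statistical Analysis Plan (SAP) will not be developed for this study, thus formal null and alternative hypothesis will not be stated". Under each primary endpoint, section 11.1 adds: "No statistical comparison will be made for this measurement". Sections 11.4.1, 11.4.2 and 11.4.4 reduce the per-subject percentages below 70 mg/dL and within 70-180 mg/dL to a median and interquartile range. Section 11.4.3 treats the number of hypoglycemic events in the same way. No confidence interval is planned. Sections 11.4.7 and 11.4.8 mark subgroup analyses and individual tabulation as not applicable. Section 11.2 says openly that the eight subjects (two type 1, six type 2) were not chosen statistically, and section 11.3 analyses everyone who starts closed loop control.

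**The concern.** A hypothesis that is to be tested needs a result that would count against it. Neither primary endpoint has one: no percentage below 70 mg/dL is defined as too high, and no percentage within 70-180 mg/dL as too low. The stated objective therefore asks for a conclusion that the primary analysis cannot give in either direction.

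The choice of summary adds a practical problem. In eight subjects, with many expected to have no time below 70 mg/dL, a median and IQR describe the unaffected majority. Hypoglycemia concentrated in one subject disappears from the primary safety result. With no individual listing and no count of affected subjects, a reader of the primary result could not recover it.

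**Working it through.** **1. The passages side by side.** Section 1.1 frames both primary objectives as hypothesis tests. Section 11 states no null or alternative hypothesis, and section 11.1 makes no comparison on either endpoint. Sections 11.4.1 to 11.4.4 give a median and IQR, with no threshold and no interval. Section 2.1 mentions a hypoglycemia rate below 0.1% as a mark of tight control, but only as background; the plan does not adopt it as a criterion.

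**2. The plan's own figure.** The only figure to reproduce is the sample size: 2 + 6 = 8, which lies within the cited range of 6-10. There is no alpha, power, effect size, SD or margin to check.

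**3. What the median and IQR show.** Order the eight per-subject percentages below 70 mg/dL. The median is the mean of the 4th and 5th values. The upper quartile lies between the 6th and 7th: by linear interpolation its position is 1 + 0.75 × 7 = 6.25. Give each affected subject x% of values below 70 mg/dL and the others 0. The column for x = 10 is illustrative.

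| Subjects affected | Median | Upper quartile | Reported if x = 10 |
|---|---|---|---|
| 0 of 8 | 0 | 0 | 0 (0-0) |
| 1 of 8 | 0 | 0 | 0 (0-0) |
| 2 of 8 | 0 | 0.25x | 0 (0-2.5) |
| 3 of 8 | 0 | x | 0 (0-10) |
| 4 of 8 | x/2 | x | 5 (0-10) |

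With one subject affected, the result is the same as for a clean run, whatever the size of x. With two or three affected, the upper quartile moves but the median does not. The event count in 11.4.3 behaves in the same way.

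**4. What subject counts would show.** Let p be the risk that a subject has at least one value below the cut-off during the session. The exact (Clopper-Pearson) two-sided 95% limits are:

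- 0 of 8: upper limit 1 − 0.025^(1/8) = 36.9%.
- 1 of 8: lower limit 1 − 0.975^(1/8) = 0.3%. The upper limit solves (1−p)^8 + 8p(1−p)^7 = 0.025, giving p = 52.7%.

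At an assumed true p of 10%, a clean run in eight has probability 0.9^8 = 43.0%; at 20% it is 0.8^8 = 16.8%.

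**5. Whether the termination criteria fill the gap.** Section 9.2 ends the study if two subjects have a Reference Glucose Value below 54 mg/dL. If all eight are treated and each has probability q of such a value, the rule is met with probability 1 − (1−q)^8 − 8q(1−q)^7. The documents give no q, so a range is assumed:

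| Assumed q | Probability that the rule is met |
|---|---|
| 5% | 5.7% |
| 10% | 18.7% |
| 20% | 49.7% |
| 30% | 74.5% |

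The probability reaches 80% only at a q of about 33%. This rule uses a different measurement and cut-off from the primary endpoint, which counts values below 70 mg/dL in the data the controller acts on (last lines of sections 5 and 11.1).

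**The case against.** The strongest reply is that this is a declared Early Feasibility Study. It disclaims formal hypotheses and comparisons and is open about its non-statistical size, so descriptive reporting in eight subjects is legitimate and the mismatch is one of wording. That stands as far as design and sample size go; nothing here calls for more subjects or for a test.

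Some of the safety reporting is also already planned. Section 10.3.3.1 and Attachment 1 class a Reference Glucose Value below 54 mg/dL as a severe or serious adverse event. Section 11.4.4 reports each such event as a percent of patients, along with the percent needing rescue medicine. Severe events would therefore surface. What is missing is a count of subjects with any value below 70 mg/dL, a count below 54 mg/dL in the endpoint's own data, and any interval.

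The limits in step 4 concern the risk per subject, which is not the primary endpoint. They show what a subject count in eight can exclude and are not a recalculation of percent time below 70 mg/dL.

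Four stronger readings are tempting, and the documents do not support them:

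- *No result at all could contradict safety.* Section 9.2 and Protocol 2, item 14, list outcomes that end the whole study, among them DKA, HHS and the investigator judging safety compromised. Under 9.2, resumption then needs FDA approval. Meeting one would be an adverse safety finding.
- *The analysed population depends on the page read.* Section 11.3 fixes it as everyone who begins closed loop control. The type 2 wording in section 5 is an editorial inconsistency and does not cause the missing criterion.
- *Superiority over open loop systems is a planned conclusion.* The statement in 6.1 that the system "will improve upon the glucose control currently achieved by open loop systems" is programme rationale; no objective, endpoint or analysis takes it up.
- *The protocol claims that this study will establish safety.* Section 4.3.12 speaks of the "potential benefit of demonstrating the safety of the FUSION systems AI based glucose control software", but calls it a potential benefit and a first step. That a clean run would be over-read is a prediction, not something the plan states.

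**Conclusion.** The point holds in limited form. The primary objectives are worded as hypothesis tests, and the primary analysis has no criterion by which either could succeed or fail. The termination criteria define adverse outcomes outside that analysis, without a stated link to the objective.

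The planned primary safety summary reads 0 (0-0) with one of eight subjects affected, and keeps a median of 0 with three of eight affected. These results assume that unaffected subjects have exactly 0% below 70 mg/dL. They do not depend on how much time an affected subject spends there.

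The exact limits treat the eight subjects as independent with a common risk, which is a simplification across two diabetes types. The rule probabilities in step 5 rest on assumed per-subject risks. The type 2 wording in section 5 is a separate, minor inconsistency.

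**What to change.** 1. In sections 1.1 and 5, reword both primary objectives as *to describe* or *to estimate* glucose control, in place of testing or assessing a hypothesis.
2. In section 11.4.4, add the number of subjects with at least one value below 70 mg/dL and the number with at least one below 54 mg/dL, in the glucose data used for the endpoint. Give each an exact 95% interval. Report these alongside the percent of patients with a Reference Glucose Value below 54 mg/dL, which is already planned as an adverse event.
3. As a separate editorial correction, make section 5 name type 1 and type 2 subjects, to match 1.1, 6.1, 11.1 and 11.3.

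The sample size, study conduct and analysis set are unchanged. The cost is wording, two counts and two intervals, and a stated claim that is less favourable to the device.
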